5.3 Study Outcomes

5.3.1 Primary Endpoints

Clinical data and the survey score of clinicians, patients, and technologists obtained directly after using the Brevera Breast Biopsy System.

5.3.1 Performance Evaluation

- Procedural information
 - Number of core biopsy samples obtained
 - Time at six different points during the Brevera Breast Biopsy System procedure.
 - Data on whether the marker dislocated (>1cm) immediately post deployment.
 - The next steps for the patient (routine screening, diagnostic surgical biopsy, therapeutic surgery, other).
 - Safety assessment include all device and procedure related AEs that occur in the study following treatment to the device.
- Biopsy sample information
 - Whether the lesion has previously been classified as a B3 lesion (uncertain malignancy potential).
- Histology evaluation
 - Histology results of each lesion.
 - Weight of the core biopsy samples obtained for each lesion
- Clinician, Technologist and Patient questionnaire

5.4 Schedule of Assessment(s)

Clinicians, Patients, and Technologists will be asked about their experience as it directly relates to the procedure that they underwent or performed. Additionally, subjects shall be evaluated from the time of the procedure through their release from the outpatient treatment facility and treated per standard of care for any adverse events which are experienced. Pathology results will be recorded once they become available.

Assessment	Baseline	Procedure
Informed Consent	Х	
Medical History*	Х	
Physical Assessment*	Х	х
Adverse Event Evaluation		Х
Procedure*		х
Questionnaires**		Х

Table 1 - Schedule of Assessments

* Per standard of care

** To be completed by Clinicians, Patients, and Technologists

5.5 Subjects

This study will recruit up to 500 females 18 years of age or older with suspicious findings on mammographic screening or diagnostic exam who are sent for biopsy.

5.5.1 Inclusion Criteria

- 1) Female aged 18 years of age or older
- 2) Subject has at least one breast imaging finding requiring biopsy for which images are available
- 3) Subject is able to understand, read and sign the study specific informed consent form after the nature of the study has been fully explained to her

5.5.2 Exclusion Criteria

- 1) Patients who, based on the physician's judgement, may be at increased risk or develop complications associated with core removal or biopsy.
- 2) Patients receiving anticoagulant therapy or may have bleeding disorders which may put the patient at increased risk of procedural complications based upon physicians judgement.

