4.1 Potential Clinical Benefit

There are no clinical benefits to the patient as the patient would have the Brevera procedure whether or not they choose to participate in this study or not. Patients will undergo the same standard procedure if they choose not to participate in this study. The results learned from this study could help future patients.

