5.1.1 Hypotheses

The hypothesis of this study is that the new breast biopsy system could provide:

- 50% Reduction in tissue needed for accurate diagnosis
- 25% Reduction in procedure time
- 50% Reduction in post-biopsy complications
- Weight of grams of tissue per a full 12 chamber
- # of samples needed to provide 1 gram of tissue
- 90% Reduction in discordant biopsies

Reduction in marker dislocation

The current standard of care includes obtaining breast biopsy core samples and verifying the samples using the mammography unit in a room which is next to the room with the biopsy table. With the Brevera procedure, the breast biopsy core samples are obtained, and the system shows images of the samples, providing instant verification.

The data will be compared to data already collected by Hologic, site aggregate data on the current standard of care, and relevant literature (see last page of protocol).

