6.2.4 Anticipated AEs/Adverse Device Effects

List of foreseeable AEs and anticipated adverse device effects, together with their likely incidence, mitigation, or treatment. These events are related to the biopsy procedure and not necessarily the devices being used for the study.

Anticipated, procedure-related AEs may include, but are not limited to, the following:

- Bruising and swelling of the breast
- Infection or bleeding at the biopsy site
- Altered breast appearance, depending on how much tissue is removed and how your breast heals
- Excessive post procedural pain at the biopsy site

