8. STATISTICAL CONSIDERATIONS

The overall sample size for this study is approximately 500 subjects. This sample is expected to be sufficient to provide a basis for providing subjective evidence of clinical performance in a clinical environment. Clinical outcomes data will be collected on all subjects, and survey responses from clinicians, patients, and technologists will be collected and analyzed.

Once all of the data has been collected and cleaned, all variables will be tabulated using descriptive statistics. Continuous variables will be presented as means and standard deviations with 95% confidence intervals, as well as medians and ranges. For categorical variables, relative frequencies and 95% confidence intervals will be provided. The data will be analyzed and compared to previous data collected by Hologic Inc, and to relevant literature.

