9.1 Data Management Procedures

This study will obtain informed consent and survey data for 500 cases. Monitoring will be conducted to ensure patient consent was obtained. Survey Data, which will serve as source data for the details of the procedure and the inclusion/exclusion criteria will be compiled from either an electronic survey form or paper form and loaded into an electronic format. Surveys will be reviewed for missing question responses/discordant answers and will be addressed as soon as missing points are noted.

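### Both exclusion criteria select on complication risk, but the hypothesised 50% cut in complications is compared with external data with no step to align eligibility

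*Combined protocol and SAP*

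**What the plan says.** Section 5.5.2 has two exclusion criteria and no others. The first excludes "Patients who, based on the physician's judgement, may be at increased risk or develop complications associated with core removal or biopsy". The second concerns anticoagulant therapy and bleeding disorders, qualified by the words "which may put the patient at increased risk of procedural complications based upon physicians judgement". Both turn on the physician's opinion and neither has a threshold. Because of its qualifier, the second may still admit some anticoagulated patients.

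Section 5.1.1 lists "50% Reduction in post-biopsy complications" among the things the system could provide. On the reference for that reduction it says: "The data will be compared to data already collected by Hologic, site aggregate data on the current standard of care, and relevant literature".

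Section 8 plans descriptive statistics with 95% confidence intervals and adds: "The data will be analyzed and compared to previous data collected by Hologic Inc, and to relevant literature". It does not repeat the site aggregate data. It does not mention comparator eligibility, restriction, matching or adjustment.

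Section 9.1 plans to compile "Survey Data, which will serve as source data for the details of the procedure and the inclusion/exclusion criteria", so eligibility information on enrolled subjects will exist. No section uses it in the complication comparison.

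**The concern.** The study population is selected on predictors of the very outcome to be compared, and nothing requires the reference population to be selected in the same way. No concurrent control group is described, although sections 1 and 5.2 call the study controlled. Any statement about fewer complications therefore rests on the external data.

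If those data include patients whom this study would exclude, the study starts with a lower expected rate whatever the device does. A plain comparison, run as written, would credit that difference to the device. A confidence interval describes sampling error and does not reveal a difference in case mix. At stake is a published statement that the system reduces complications, part of which would describe who was biopsied and not how.

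**Working it through.** **The plan's own figure.** There is none to reproduce. The documents give a target of 50% but no baseline complication rate, no share of patients expected to be excluded and no comparator eligibility. Everything below except the 50% is an assumption.

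**Inputs (assumed)**
- f: share of usual biopsy patients in the higher-risk group
- RR: that group's relative risk of any complication
- e: share of that group enrolled in the study despite the criteria
- s: share of that group excluded from the comparator data

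**Formulas**
- Higher-risk share in the study: fs = f·e / (1 − f(1 − e))
- Higher-risk share in the comparator: fc = f(1 − s) / (1 − f·s)
- Apparent reduction with no device effect: 1 − [1 + fs(RR − 1)] / [1 + fc(RR − 1)]

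**Results at f = 10%**

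| Scenario | RR 1.5 | RR 2 | RR 3 |
|---|---|---|---|
| Comparator unrestricted, none enrolled (s = 0, e = 0) | 4.8% | 9.1% | 16.7% |
| Comparator unrestricted, half enrolled (s = 0, e = 0.5) | 2.3% | 4.3% | 7.9% |
| Comparator excludes half, none enrolled (s = 0.5, e = 0) | 2.6% | 5.0% | 9.5% |
| Same share excluded on both sides | 0% | 0% | 0% |

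For RR = 2 in the first row: fs = 0 and fc = 0.10, so 1 − 1/1.10 = 9.1%. In the second row: fs = 0.05/0.95 = 0.0526, so 1 − 1.0526/1.10 = 4.3%.

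**Effect on the 50% target.** The true device reduction that would show as 50% is 1 − 0.5 × [1 + fc(RR − 1)] / [1 + fs(RR − 1)]. At f = 10%, RR = 2 and unrestricted comparators, this is 1 − 0.5 × 1.10 = 45.0% with none enrolled, and 1 − 0.5 × 1.10/1.0526 = 47.75% with half enrolled. At RR = 3 with none enrolled it is 1 − 0.5 × 1.20 = 40.0%.

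**Which RR is plausible.** The second criterion bears mainly on bleeding. Section 6.2.4 lists "Infection or bleeding at the biopsy site" beside bruising, swelling, altered appearance and pain. If bleeding makes up a share b of complications, the relative risk of any complication is 1 + b(RR for bleeding − 1). A bleeding RR of 3 with b = 0.25 to 0.5 gives 1.5 to 2. This covers the second criterion only. The first concerns any complication, so the overall RR could be higher.

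**Sensitivity.** With unrestricted comparators and none enrolled, f = 5% and RR = 2 gives 1 − 1/1.05 = 4.8%, and f = 20% and RR = 3 gives 1 − 1/1.4 = 28.6%. An extreme pair, f = 30% and RR = 5, gives 1 − 1/2.2 = 54.5%. The result follows the inputs chosen, and the documents supply none of them.

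**The case against.** The strongest reply is that the deciding fact cannot be seen. The literature list that section 5.1.1 places on the last page, the sponsor's earlier data, the site data and the Instructions for Use are not in the available text, and their absence is no fault of the plan. The comparators may carry equivalent exclusions. This stands: no bias has been shown. What remains is that no planned step would show whether it is there.

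Second, the shift may be small beside sampling error. Suppose a fixed comparator rate of 5% and 12 events among 500 subjects. The Wilson 95% interval for the apparent reduction then runs from about 17% to 72%. At a comparator rate of 10% and 25 events it is about 27% to 66%. A move from 45% to 50% lies well inside both. This also stands, and it limits the weight of the point. But selection of this kind pushes in one direction and does not shrink with more subjects.

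Third, eligibility is not the only obstacle. Section 6.2.1 ends adverse event assessment at discharge, so a comparator with longer follow-up would differ even after alignment. That is true, and the change below does not cure it.

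A reader might go further and infer that the comparison is biased as planned, that selection could account for the whole 50%, or that the primary analysis fails. The documents support none of these. Comparator eligibility is unknown. At f = 10% and RR up to 3 the effect is well short of 50%. The analysis is descriptive, the hypothesis says only what the system could provide, and it is unclear whether complications fall under the clinical data named in the primary endpoint (section 5.3.1, Primary Endpoints).

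**Conclusion.** The concern holds in conditional form. Both exclusion criteria lower the expected complication rate, and the plan compares that rate with external data without aligning eligibility or limiting the conclusion. Wherever a comparator is less restricted, part of the apparent reduction is selection; where the exclusions match, that part is zero. In the first scenario of the table it is 4.8% to 16.7% over RR 1.5 to 3, and about half that if half of the higher-risk group is enrolled. It would be wrong to read any of these values as a ceiling, since f and RR are not in the documents and the first criterion covers any complication. The consequence is a descriptive comparison that may be partly misattributed. It is worth correcting, with medium confidence, and it is not a reason to alter the exclusion criteria.

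**What to change.** Add to section 8:

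1. A table of the eligibility criteria of each external source used for complications.
2. Where sites or the sponsor can supply them, reference complication rates restricted to patients without anticoagulant therapy or a bleeding disorder, compared with study subjects restricted in the same way. The study side needs the restriction too, because the second criterion can admit some such patients. The eligibility data planned in section 9.1 may serve; add the two items to the forms only if they are missing.
3. Where alignment is not possible, a rule that the difference is reported descriptively, is not presented as a device effect on complications, and supports conclusions only for patients not judged at increased risk. This will usually apply to the first criterion, a judgement that aggregate or published data cannot reproduce.

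Optionally, keep a per-site count of patients excluded under each criterion. Section 4.1 does not establish that this is feasible: its statement that "the patient would have the Brevera procedure whether or not they choose to participate in this study" concerns patients who decline, not those excluded.

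The cost is a table, a more specific data request and a few lines of text. The downside is a narrower claim and fewer usable comparators, since many aggregate or published sources will not allow the restriction.

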5.5.3 Informed Consent & Enrollment Procedures

Although the device in this study has received CE Mark for commercial use, informed consent shall be obtained in writing from the subject or their legally authorized representative and the process shall be documented before any procedure specific to the clinical study is applied to the subject, in order to collect procedural specific data.

The general process for obtaining informed consent shall:

- ensure that the Principal Investigator or his/her authorized designee conducts the informed consent process;
- include all aspects of the clinical study that are relevant to the subject's decision to participate throughout the clinical study;
- avoid any coercion or undue improper influence on, or inducement of, the subject to participate;
- not waive or appear to waive the subject's legal rights;
- use native non-technical language that is understandable to the subject;
- provide time for the subject to read and understand the informed consent form and to consider participation in the clinical study;
- include personally dated signatures of the subject and the principal investigator or an authorized designee responsible for conducting the informed consent process;
- provide the subject with a copy of the signed and dated informed consent form and any other written information; and,
- ensure the patient is aware that the de-identified study case report forms and images are being sent to Hologic, in the United States.

Upon signing the Informed Consent Form, the subject is considered enrolled in the study.

5.5.4 Subject Withdrawal/Discontinuation

A study subject will be discontinued from participation in the study if:

- The Investigator feels that the subject can no longer fully comply with the requirements of the study or if any of the study procedures would not be in the best interest of the subject.
- The subject wishes to withdrawn their consent for participation in the study.

5.6 Study Duration

Study Start:	Q1/2017
Enrollment Completion:	Q3/2017
Last Patient, Last Visit:	Q3/2017
Final Report:	Q4/2017

6. STUDY PROCEDURES

The study will collect de-identified case report form data and patient images from biopsy procedures. This will include collection of images from the prior exam leading up to the Brevera Breast Biopsy System Procedure. The biopsy procedures will be done consistent with current clinician direction/standard of care. There are no special requirements under this protocol for how biopsies are performed.

Prior to use of the new Brevera Breast Biopsy System, normal applications training will take place in order to train the users on new features and quality control testing.

6.1 Efficacy Assessment

The breast biopsy systems being evaluated during the course of this study are all commercially available. All devices will have CE mark prior to being utilized clinically.

[figure not shown]
6.2 Safety/Device Assessment

6.2.1 Adverse Events

An adverse event (AE) is any untoward medical occurrence, unintended disease or injury or any untoward clinical signs (including an abnormal laboratory finding) in subjects, users or other persons whether or not related to the study medical device. Each AE is considered either anticipated or unanticipated as described below. The site is required to report all device and procedure related AEs that occur in the study following treatment to the device manufacturer, Hologic, Inc.

AE Reporting Flow Chart:

The time-period for the assessment of the occurrence of an AE will begin at the time of consent until the subject has been discharged and will be based on changes in the subject's physical examination, laboratory results and/or signs and symptoms. AEs are to be monitored until they are resolved or clearly determined to be a stable or chronic condition or due to an undercurrent illness. Medical care will be provided, as defined in the informed consent, for any AE related to study participation.

There are two types of AEs: anticipated or unanticipated. Subjects who experience any untoward aftereffects are instructed to contact their Investigator or study coordinator immediately. The Investigator must determine both the intensity of the AE and the event's relationship to the Clinical System.

AE Severity Classification: Severity will be defined according to the following criteria:

- Mild Awareness of event, but easily tolerated
- Moderate Discomfort enough to cause some interference with activities of daily living (ADL)
- Severe Incapacitating, with an inability to perform activities of daily living (ADL)

Life threatening events, events where the subject was at risk of death, are serious AEs and must be reported in accordance with the procedures and timelines in this protocol.

AE Relationship Classification: Relationship to study product use will be determined as follows:

• **Not Related** - relationship to the device or procedures can be excluded when:

- The event is not a known side effect of the product category the device belongs to or of similar devices and procedures
- \circ The event has no temporal relationship with the use of the device or the procedures
- The serious event does not follow a known response pattern to the medical device (if the response pattern is previously known) and is biologically implausible
- The discontinuation of the medical device application or the reduction of the level of activation/exposure- when clinically feasible- and reintroduction of its use (or increase of the level of activation/exposure), does not impact the serious event
- the event involves a body-site or an organ not expected to be affected by the device or procedure
- the serious event can be attributed to another cause (e.g. an underlying or concurrent illness/ clinical condition, an effect or another device, drug, treatment or other risk factors)
- the event does not depend on a false result given by the study device used for diagnosis when applicable
- \circ $\hfill\hfilt$
- in order to establish the non-relatedness, not all the criteria listed above might be met at the same time, depending on the type of device/ procedures and the serious event.
- **Unlikely** The relationship with the use of the device seems not relevant and/or the event can be reasonably explained by another cause, but additional information may be obtained.
- **Possible** The relationship with the use of the device is weak but cannot be ruled out completely. Alternative causes are also possible (e.g an underlying or concurrent illness/ clinical condition/ or and an effect of another device, drug or treatment), Cases where relatedness cannot be assessed or no information has been obtained should also be classified as possible.
- **Probable** the relationship with the use of the study device seems relevant and/or the event cannot reasonably be explained by another cause, but additional information may be obtained
- **Causal Relationship** the serious event is associated with the device or with the procedures beyond reasonable doubt when:
 - The event is a known side effect of the product category the device belongs to or of similar devices and procedures
 - \circ The event has a temporal relationship with the device application/use or procedures
 - the event involves a body-site or organ that:
 - the device or procedures are applied to
 - the device or procedures have an effect on
 - the serious event follows a known response pattern to the medical device (if te response pattern is previously known)
- the discontinuation of the medical device application (or reduction of the level of activation/exposure) and reintroduction of its use (or increase of the level of activation/exposure), impact on the serious event (when clinically feasible)
- Other possible causes (e.g. an underlying or concurrent illness/ clinical condition or/and an effect of another device, drug or treatment) have been adequately ruled out

- Harm to the subject is due to error in use
- the event depends on a false result given by the device used for diagnosis, when applicable
- in order to establish the relatedness, not all the criteria listed above might be met at the same time, depending on the type of device/procedures and the serious event

AE Outcome Classification: Outcome of the event will be defined according to the following:

- **Resolved** The event is resolved and is no longer present
- Not resolved The event has not yet been resolved
- **Resolved with sequelae** The event has resolved, but with an after affect possibly due to disease, injury, treatment or procedure
- Fatal The event resulted in subject death

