4.2 Anticipated Adverse Device Effect(s)

Common risks associated with the use of any commercial biopsy system are limited to the region surrounding the biopsy site and include:

- Bruising and swelling of the breast
- Infection or bleeding at the biopsy site
- Altered breast appearance, depending on how much tissue is removed and how your breast heals
- Excessive pain following the procedure at the biopsy site

All of the incidents above are related to the biopsy procedure and not necessarily the devices themselves.

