6.3 Reporting Procedures

6.3.1 Investigator Reporting

The Investigator at each participating center is ultimately responsible for reporting applicable AEs to Hologic. The information to be reported on the AE CRF and should include the start date of the AE, treatment, resolution, and assessment of both the seriousness and the relationship to the device and should be captured on the AE CRF. The Investigator should report all AEs to the EC/IRB, as required.

If there is a device malfunction or other observation (deficiency), the Investigator should notify Hologic immediately via the normal complaint procedure for commercially available devices, indicate if the observation resulted in an AE, and indicate if complications are related to the device, procedure or underlying disease.

In the event of a suspected observation or device problem, a field technician will be dispatched to the site to resolve the problem. If the field engineer cannot resolve the problem, the device may be returned to Hologic/Plexus for analysis.

Hologic Contact Information:

For Germany, incidents will be reported to the Competent Authorities according to the German Safety Plan for Medical Devices (MPSV). This means that incidents (an incident is any malfunction, any failure or deterioration in the characteristics or performance of a medical device as well as any inaccuracy in the labelling or instructions for use which has led, or could have led, directly or indirectly, to the death or serious deterioration in the state of health of a patient or user or another person) that occurred in Germany, a recall of the medical device implemented in Germany, and incidents that occurred outside the European Economic Area (EEA) and led to corrective measures that are also relevant to medical devices marketed within the EEA, will be reported to the BfArM by the Sponsor and/or Investigator using the applicable forms.

Incidents should be reported without delay in accordance with the required urgency of attention but in any case within a maximum of 30 days of these becoming known. If a delay is likely to cause danger, the notification shall be made immediately. Recalls and incidents outside the EEA as described above shall be reported immediately. Other recalls and incidents that occurred outside the EEA shall be reported at the latest by the time of implementation of any measures.

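### The safety outcome covers device- and procedure-related adverse events, but the relatedness scale and the described AE form do not rate the procedure consistently, so biopsy complications can be graded differently and cannot be separated by cause

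*Combined protocol and SAP*

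**What the plan says.** Section 5.3.1 (Performance Evaluation) sets the scope of the safety outcome: "Safety assessment include all device and procedure related AEs that occur in the study following treatment to the device". Section 6.2.1 gives sites a matching duty: "The site is required to report all device and procedure related AEs that occur in the study following treatment to the device manufacturer". Section 10.2 lists failure to report events related to the Brevera procedure or device as a protocol deviation.

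The rating instructions are narrower. Section 6.2.1 says: "The Investigator must determine both the intensity of the AE and the event's relationship to the Clinical System". It then introduces the scale as one of relationship to use of the study product. The lowest grade, *Not Related*, applies where "relationship to the device or procedures can be excluded when". The next grade up, *Unlikely*, is worded "The relationship with the use of the device seems not relevant and/or the event can be reasonably explained by another cause". Section 6.3.1 says that the AE report should include "assessment of both the seriousness and the relationship to the device".

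On the complications the study expects (bruising and swelling, infection or bleeding, altered appearance, excessive pain), section 4.2 says: "All of the incidents above are related to the biopsy procedure and not necessarily the devices themselves". Section 6.2.4 repeats this.

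**The concern.** The outcome has two parts, device and procedure, but the instrument that assigns events to it mostly asks about one. The mismatch falls on the main safety events, because the protocol itself assigns the expected complications to the procedure and leaves the device's part open.

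Two things are at stake. The first is consistency. Up to 10 sites in six countries will grade these events, and the wording supports more than one grade for the same event. The second is interpretation. Section 5.1.1 hypothesises a reduction in post-biopsy complications, and sections 5.1.1 and 8 plan a comparison with the sponsor's earlier data, site aggregate data and literature. No concurrent arm is rated on the same scale, so inconsistent ascertainment here would not cancel against the comparator.

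**Working it through.** The protocol states no figure on this point, so the check compares its wording.

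**Step 1: what each grade in 6.2.1 refers to.**

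| Grade | Referent | Relevant wording |
|---|---|---|
| *Not Related* | device or procedures | several criteria are written for a serious event |
| *Unlikely* | device only | explanation by another cause is enough by itself (and/or) |
| *Possible* | device only | also the default when relatedness cannot be assessed |
| *Probable* | device only | |
| *Causal Relationship* | device or procedures | lead sentence is written for a serious event, beyond reasonable doubt |

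**Step 2: pass one event through the scale.** Take a non-serious bruise after biopsy that the investigator, following 4.2, attributes to the procedure.
- *Not Related* does not fit, because the procedure cannot be excluded.
- *Unlikely* can fit, if the procedure is taken as the other cause that explains the event.
- *Causal Relationship* can also fit: the event is a known side effect, follows the procedure in time and lies at the treated site. The lead sentence, however, speaks of a serious event.
- An event that is probably but not certainly due to the procedure has no grade worded for it, because the three intermediate grades do not mention the procedure.

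Two careful investigators can thus record grade 2 and grade 5 for the same event.

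**Step 3: can another field recover the cause?** Section 6.3.1 does ask whether complications relate to device, procedure or underlying disease. That request sits in the paragraph on malfunctions and deficiencies, which go through the complaint route. It does not apply to every AE. No section calls for a procedure rating on each event.

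**Step 4: what is reported and counted.** Section 6.2.1 requires device- and procedure-related AEs to be reported to the sponsor. Section 6.3.1 speaks of applicable AEs. The investigator agreement in 14.1 asks for all AEs, but according to the protocol, which leads back to 6.2.1. No section states which of the five grades count as related.

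**Step 5: can the effect be sized?** Let *m* be the share of true complications not counted in this study, *c* the share not counted in the external data, and *R* the true ratio of complication rates (Brevera to comparator). Then

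observed ratio = *R* × (1 − *m*) / (1 − *c*).

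The documents give no value for *m*, *c* or the complication rate. If *m* = *c* the comparison is undistorted. If *m* > *c* it favours Brevera, and if *m* < *c* it goes the other way. Neither size nor direction can be derived.

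**The case against.** The strongest reply is that no rule drops any event. The safety outcome, the reporting duty and the deviation list all include procedure-related events and refer to no grade, so a bleed attributed to the biopsy is in scope whatever its device grade. This stands. A reader might infer that events graded *Unlikely* are lost from the count, but that presumes a cut-off the protocol never sets.

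Second, where the scale gives examples of other causes it lists illness, or another device, drug or treatment, and never the index procedure. Both end grades put device and procedures together, and Brevera is itself the biopsy instrument. This makes *Unlikely* the less natural reading for a biopsy bleed. It does not exclude it, because nothing states the restriction and sections 4.2 and 6.2.4 separate procedure from device.

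Third, *Causal Relationship* can take procedure events. Several of its criteria say event and not serious event, not all need be met, and unassessable cases default to *Possible*. This also stands, and it limits the risk of under-counting. It does not supply an intermediate grade for the procedure or a field that separates the two causes.

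Fourth, the blank form was not available, and the AE reporting flow chart announced in 6.2.1 does not appear in the text reviewed. The point about the form rests on the description in 6.3.1, which may not be the complete field list.

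**Conclusion.** The mismatch holds on the text. An AE form built as 6.3.1 describes, completed with the scale in 6.2.1, would not identify procedure-related events consistently and could not separate them from device-related ones. The disagreement the wording permits runs from grade 2 to grade 5. It does not span the whole scale, since *Not Related* is ruled out for an event the procedure caused.

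A reader might go further and infer that the scale could by itself produce the hypothesised reduction in complications. The documents do not support that. It would need an assumed share of lost events, a fully counted comparator and an exclusion rule, and none of these is given. The planned analysis is descriptive, with 95% confidence intervals and no decision threshold. Under-counting is therefore a risk of unknown size and not a demonstrated bias.

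The conclusion assumes that the form follows 6.3.1 and that the missing flow chart adds no procedure rating. It merits correction because the comparison is external, and because events a site judged unrelated and never reported cannot readily be re-graded later.

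**What to change.** In 6.2.1 and on the AE form:

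1. Rate every AE twice, once for relationship to the biopsy procedure and once for relationship to the Brevera device.
2. Word all five grades for each referent, and for non-serious as well as serious events.
3. State which grades count as related for the safety outcome.
4. Reconcile the reporting scope in 6.2.1 (related AEs) with that in 14.1 (all AEs).
5. Base the complication rate on events related to either the procedure or the device, matching 5.3.1, and report the device rating separately.

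The cost is one extra form field and a wording edit, best made before data collection. The downside is that the reported complication rate may be higher.
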